### 8.6.3. Pregnancy

Any pregnancies reported during the study will be summarized in case narratives. Any pregnancy complication or elective termination of a pregnancy for medical reasons will be recorded as an AE or SAE and included in summaries and listings of AEs/SAEs.

### 8.6.4. Planned Statistical Analyses of Safety Endpoints

#### 8.6.4.1. Vital Signs and ECGs

Statistical Analysis of Safety Endpoints
Endpoints

 
• Change from baseline in Pulse rate
 
• Change from baseline in Systolic BP
 
• Change from baseline in Diastolic BP
 
• Change from baseline in QTc (F)
 
• Change from baseline in PR Interval
 
• Change from baseline in Heart Rate (ECG)
 

Model Specification, Checking, Results Presentation and SAS code

 
• Data up to Week 24 for these endpoints will be analyzed using the same methodology as trough FEV1 in Section 7.1.6 using the on-treatment (de jure) type estimand and unpooled data.
 
• Treatment comparisons 1) and 2) only as defined in Section 7 will be presented.
 

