4.3. Type and Number of Subjects

Patients with inadequately controlled asthma (i.e. patients with an ACQ-6 score ≥ 1.5 prior to enrolment at Visit 2) despite treatment with maintenance asthma medication.

The total number of randomized subjects required is approximately 2250, with 375 subjects randomized to each of the 6 double-blind treatment arms (to ensure approximately 337 evaluable subjects per treatment arm; see Section 9.2.1). Randomization will be stratified by pre-study ICS treatment strength (mid, high) at screening to ensure treatment balance within each stratum.

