6.2. Treatment Assignment

Subjects will be assigned to study treatment in accordance with the randomization schedule. The randomization code will be generated by GSK using a validated computerized system. Subjects will be randomized using an IRT system (RAMOS NG). The study will use central-based randomization to allocate treatments (see [Appendix 7](#) for country-specific requirements). Once a randomization number is assigned to a subject it cannot be reassigned to any other subject in the study.

Following the 2-week stabilization period and subject to satisfying all eligibility criteria, subjects will be stratified by pre-study ICS treatment dosage strength (mid, high) at screening and randomized 1:1:1:1:1:1 to one of the following six double-blind treatments for the duration of the treatment period:

- FF/UMEC/VI 100/62.5/25 mcg QD
- FF/UMEC/VI 200/62.5/25 mcg QD
- FF/UMEC/VI 100/31.25/25 mcg QD
- FF/UMEC/VI 200/31.25/25 mcg QD
- FF/VI 100/25 mcg QD
- FF/VI 200/25 mcg QD

The duration of double-blind treatment for each subject is a minimum of 24 weeks and a maximum of 52 weeks (see [Section 4.2](#)); on the morning of each scheduled clinic study visit, subjects will refrain from taking their morning dose of study treatment until instructed to do so by clinic personnel. Study treatment will be taken at the clinic at approximately the same time of day as taken at the Enrolment Visit (Visit 2). On the other days during the treatment period (i.e. "non-clinic days"), subjects will be instructed to take their study treatment each morning at approximately the same time. Each Investigator will be provided with sufficient supplies to conduct the trial. Additional

treatment packs will be supplied as needed to the sites. Details of how to use the IRT system (RAMOS NG) to randomize subjects and manage study treatment supplies (including dispensing) is provided in the RAMOS NG IRT manual and SRM.

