9.2. Sample Size Considerations

9.2.1. Sample Size Assumptions

Sample size calculation is based on the primary efficacy endpoint of mean change from baseline in trough FEV₁ at the end of the 24-week treatment period.

A total of 2250 randomized subjects are required for this study, with 375 subjects in each of the six double-blind treatment groups:

- FF/VI 100/25 mcg
- FF/VI 200/25 mcg
- FF/UMEC/VI 100/31.25/25 mcg
- FF/UMEC/VI 200/31.25/25 mcg
- FF/UMEC/VI 100/62.5/25 mcg
- FF/UMEC/VI 200/62.5/25 mcg

Assuming 10% missing data on spirometry at the end of the 24-week treatment period, due to early withdrawal from study, approximately 337 subjects per treatment group should have trough FEV₁ data available for the analysis.

The standard deviation for the mean change from baseline in trough FEV₁ at the end of the 24-week treatment period is estimated to be 400 mL based on previous asthma studies. The proposed sample size of n=337 per treatment group should provide 90% power, assuming a difference of 100 mL, based on a two sample t-test with a two sided significance level of 0.05 for each of the two primary comparisons of interest for each UMEC dose.

For the target population, it is assumed that the mean exacerbation rate is 2 per year for the control group FF/VI; this was based on a review of previous FF/VI asthma exacerbation study conducted by GSK and Tio asthma studies conducted by Boehringer Ingelheim. The proposed sample size of 750 randomized subject per arm (based on the treatment comparison of combined triple therapies and combined dual therapies with both FF doses) should have approximately 95% power if the true reduction in exacerbation

rate for triple therapy vs. dual therapy is 20%. The calculation assumes the number of exacerbations per year follows a negative binomial distribution [Keene 2007], with a dispersion parameter $k=0.7$ based on a previous FF/VI asthma exacerbation study, and assumes the following accelerative recruitment rate per week over a period of 39 weeks:

[figure not shown]
- 3.5 weeks at 15 patients/week
- 4.5 weeks at 25 patients/week
- 4.5 weeks at 35 patients/week
- 4.5 weeks at 45 patients/week
- 4.5 weeks at 55 patients/week
- 4.5 weeks at 70 patients/week
- 13 weeks at 90 patients/week

The duration of the treatment period is variable but will be at least 24 weeks and up to a maximum of 52 weeks, with the end of study date being established once the last subject has been randomized.

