## 7. EFFICACY ANALYSES

All efficacy analyses will evaluate the “de facto” type estimand (see Section 7.1.4 for details) based on the ITT population, including data collected during the study, both on- and post-treatment without imputation, unless otherwise specified.

To demonstrate the benefit of UMEC when added to FF/VI treatment arms with the same FF dose, the primary comparisons of interest for the primary efficacy endpoint are:

- 1) The replicate efficacy for UMEC 62.5 mcg dosage:
  - FF/UMEC/VI 100/62.5/25 mcg vs. FF/VI 100/25 mcg
  - FF/UMEC/VI 200/62.5/25 mcg vs. FF/ VI 200/25 mcg
- 2) The replicate efficacy for UMEC 31.25 mcg dosage:
  - FF/UMEC/VI 100/31.25/25 mcg vs. FF/VI 100/25 mcg
  - FF/UMEC/VI 200/31.25/25 mcg vs. FF/ VI 200/25 mcg

Other pairwise treatment comparisons of interest consist of the following assessments for the primary efficacy endpoint:

- 3) Triple therapy with low dose FF vs. dual therapy with high dose FF:
  - FF/UMEC/VI 100/62.5/25 vs. FF/VI 200/25
  - FF/UMEC/VI 100/31.25/25 vs. FF/VI 200/25
- 4) The impact of increasing FF dose in triple therapy:
  - FF/UMEC/VI 200/62.5/25 vs. FF/UMEC/VI 100/62.5/25
  - FF/UMEC/VI 200/31.25/25 vs. FF/UMEC/VI 100/31.25/25
- 5) The impact of increasing UMEC dose in triple therapy:
  - FF/UMEC/VI 100/62.5/25 vs. FF/UMEC/VI 100/31.25/25
  - FF/UMEC/VI 200/62.5/25 vs. FF/UMEC/VI 200/31.25/25
- 6) The benefit of FF 200 containing therapies over FF/VI 100/25, the asthma medication used prior to randomization, during the stabilization phase:
  - FF/VI 200/25 vs. FF/VI 100/25
  - FF/UMEC/VI 200/31.25/25 vs. FF/VI 100/25
  - FF/UMEC/VI 200/62.5/25 vs. FF/VI 100/25

To allow evaluation of the effect of FF/UMEC/VI on non-lung function efficacy endpoints, including the key secondary efficacy endpoint on moderate/severe exacerbations, for each fixed UMEC dose, the data from the two FF/UMEC/VI arms will be pooled and compared to the pooled data from the two FF/VI arms.

- 7) Benefit of UMEC added on to FF/VI: UMEC 62.5 mcg dosage:
  - FF/UMEC/VI (100/62.5/25 and 200/62.5/25) vs. FF/VI (100/25 and 200/25)
- 8) Benefit of UMEC added on to FF/VI: UMEC 31.25 mcg dosage:
  - FF/UMEC/VI (100/31.25/25 and 200/31.25/25) vs. FF/VI (100/25 and 200/25)

The pooled analyses will provide a more precise overall estimate for the treatment effect size of the addition of UMEC to FF/VI.

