## 8. SAFETY ANALYSES

All safety analyses will be based on the ITT population. On-treatment safety data collected at scheduled clinic visits will be summarized and analyzed by treatment and by visit, unless otherwise specified. On-treatment adverse events and post-treatment adverse events will be summarized separately. All data will be listed, unless otherwise specified.

An overview of the planned analyses is provided below. The full details of safety analysis data displays are presented in [Appendix 10: List of Data Displays](#)

	Absolute			Change from Baseline		
	Summary		Individual	Summary		Individual
	T	F	L	T	F	L
Exposure						
Extent of Treatment Exposure (unpooled and pooled FF doses)	Y					
Post-Treatment Duration on Study	Y					
Adverse Events (AEs)						
Relationship of AE System Organ Class, Preferred Term and Verbatim Text			Y 			
AEs during screening/ run-in period	Y		Y 			
AEs during stabilization period	Y		Y 			
Overview of On-Treatment AEs	Y					
On-Treatment AEs	Y		Y			
On-Treatment AEs adjusted for exposure (per thousand person-years)	Y					
On-Treatment AEs in the respiratory, thoracic and mediastinal disorders SOC	Y					
On-Treatment AEs in the respiratory, thoracic and mediastinal disorders SOC (per thousand person-years)	Y					
Post-Treatment AEs during the study	Y		Y			
Post-Study AEs	Y		Y			
On Treatment AEs during Weeks 1-24	Y					
On Treatment AEs during Weeks 1-36 for participants with ≥ 36 weeks of planned treatment exposure	Y					
On Treatment AEs during Weeks 1-52 for participants with 52 weeks of planned treatment	Y					

	Absolute			Change from Baseline		
	Summary		Individual	Summary		Individual
	T	F	L	T	F	L
exposure						
On-Treatment Drug-Related AEs	Y					
On-Treatment Drug-Related AEs during the study adjusted for exposure (per thousand person-years)	Y					
Post-Treatment Drug-Related AEs	Y					
On-Treatment SAEs	Y					
On-Treatment SAEs adjusted for exposure (per thousand person-years)	Y					
Post-Treatment SAEs	Y					
Non-fatal SAEs			Y			
Fatal SAEs			Y			
On-Treatment Drug-Related SAEs	Y					
On-Treatment Drug-Related SAEs adjusted for exposure (per thousand person-years)	Y					
On-Treatment SAEs during Weeks 1-24	Y					
On-Treatment SAEs during Weeks 1-36 for participants with $\geq$ 36 weeks of planned treatment exposure	Y					
On-Treatment SAEs during Weeks 1-52 for participants with 52 weeks of planned treatment exposure	Y					

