## 11.10.8. Safety Tables

Safety: Tables					
No.	Population	IDSL ID / Example Shell	Title	Programming Notes	Deliverable [Priority]
Exposure					
3.1.	ITT	EX1	Summary of Exposure to Fluticasone/Salmeterol 250/50 via the DISKUS DPI During the Run-in Period		SAC
3.2.	ITT	EX1	Summary of Exposure to FF/VI 100/25 via the ELLIPTA DPI During the Stabilization Period		SAC
3.3.	ITT	EX1	Summary of Exposure		SAC [1]
3.4.	ITT	EX1	Summary of Exposure – Pooled FF Doses		SAC
3.5.	ITT	SAFE_T1	Summary of Post-Treatment Duration		SAC
Adverse Events					
3.6.	ITT	AE1	Summary of Adverse Events During Screening/Run-in Period	Include total column	SAC
3.7.	ITT	AE1	Summary of Adverse Events During Stabilization Period	Include total column	SAC
3.8.	ITT	AE13	Overview of On-Treatment Adverse Events		SAC [1]
3.9.	ITT	SAFE_T2	Overview of On-Treatment Adverse Events per Thousand Person-Years		SAC
3.10.	ITT	AE1	Summary of On-Treatment Adverse Events		SAC [1]
3.11.	ITT	SAFE_T3	Summary of On-Treatment Adverse Events per Thousand Person-Years		SAC
3.12.	ITT	AE1	Summary of On-Treatment Adverse Events in the Respiratory, Thoracic and Mediastinal Disorders System Organ Class (Primary or Secondary)		SAC
3.13.	ITT	SAFE_T3	Summary of On-Treatment Adverse Events in the Respiratory, Thoracic and Mediastinal Disorders System Organ Class (Primary or Secondary) per Thousand Person-Years		SAC

Safety: Tables					
No.	Population	IDSL ID / Example Shell	Title	Programming Notes	Deliverable [Priority]
3.14.	ITT	AE1	Summary of Post-Treatment Adverse Events		SAC
3.15.	ITT	AE1	Summary of Post-Study Adverse Events		SAC
3.16.	ITT	AE1	Summary of On-Treatment Adverse Events Up to Week 24		SAC
3.17.	ITT	SAFE-T3	Summary of On-Treatment Adverse Events Up to Week 24 per Thousand Person-Years		SAC
3.18.	ITT	AE1	Summary of On-Treatment Adverse Events Up to Week 36 for Subjects with $\geq 36$ Weeks of Planned Treatment Exposure		SAC
3.19.	ITT	SAFE-T3	Summary of On-Treatment Adverse Events Up to Week 36 for Subjects with $\geq 36$ Weeks of Planned Treatment Exposure per Thousand Person-Years		SAC
3.20.	ITT	AE1	Summary of On-Treatment Adverse Events for Subjects with 52 Weeks of Planned Treatment Exposure		SAC
3.21.	ITT	SAFE-T3	Summary of On-Treatment Adverse Events for Subjects with 52 Weeks of Planned Treatment Exposure per Thousand Person-Years		SAC
3.22.	ITT	AE1	Summary of On-Treatment Drug-Related Adverse Events		SAC [1]

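### The ECG and vital-sign models in SAP 8.6.4.1 report UMEC only within each FF dose, so each interval is about 41% wider than the pooled-FF contrast the same model can give

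*SAP*

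**What the plan says.** SAP 8.6.4.1 lists six safety endpoints for formal modelling: change from baseline in pulse rate, systolic BP, diastolic BP, QTcF, PR interval and ECG heart rate. They use on-treatment, unpooled data up to Week 24 and the trough FEV1 model of Section 7.1.6. The output is then restricted: "Treatment comparisons 1) and 2) only as defined in Section 7 will be presented".

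In SAP Section 7, comparisons 1) and 2) are the within-FF pairs for UMEC 62.5 and UMEC 31.25, four in all. Comparisons 7) and 8) set the two triple arms at one UMEC dose against the two FF/VI arms. Section 7 prints the LSMESTIMATE coefficients for these and says of pooling: "The pooled analyses will provide a more precise overall estimate for the treatment effect size of the addition of UMEC to FF/VI". That sentence follows text about non-lung-function efficacy endpoints. Even so, trough FEV1, whose primary comparisons are within FF dose, also receives a pooled-FF analysis (Section 7.1.6; Table 2.19).

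Among the safety displays, the Section 8 overview marks one item as pooled over FF dose, "Extent of Treatment Exposure (unpooled and pooled FF doses", and Section 11.10.8 has one matching title, Table 3.4: "Summary of Exposure – Pooled FF Doses". AE, AESI and MACE displays are counts, percentages and rates per thousand person-years. The notes to the Section 8 overview name only vital signs and ECG parameters for statistical analysis.

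**The concern.** The safety objective in Protocol Section 3 compares FF/UMEC/VI with FF/VI. For ECG and vital signs, the SAP answers it with two separate estimates per UMEC dose, each from one pair of arms, and never combines them. Any UMEC effect on QTcF or heart rate is likely to be small, so interval width largely determines what the study report can rule out. A tighter estimate of the average UMEC effect needs no further data and no further model, and the plan already takes that step for its primary lung-function endpoint.

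**Working it through.** **The plan's own sizing, reproduced first.** The documents give no precision figure for safety, so the check starts from the trough FEV1 calculation in Protocol 9.2.1: "should provide 90% power, assuming a difference of 100 mL", SD 400 mL, "based on a two sample t-test with a two sided significance level of 0.05".

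- n per arm = 2 × (1.960 + 1.282)² × (400/100)² = 336.2, rounded up to 337.
- Power at n = 337 is 0.9006 by the normal approximation and 0.8998 by the exact t-test. The stated 90% reproduces.
- Allowing for 10% missing: 337/0.9 = 374.4, rounded up to 375; 6 × 375 = 2250.

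**Inputs for the safety contrast.**

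- Planned arm size: "with 375 subjects randomized to each of the 6 double-blind treatment arms" (Protocol 4.3).
- Allocation: "randomized 1:1:1:1:1:1 to one of the following six double-blind treatments" (Protocol 6.2).
- Number randomized, from the region table in SAP 5.4: 766 + 643 + 399 + 631 = 2439, or about 406 per arm if balanced.
- Coefficients in display order (SAP Section 7): UMEC 62.5 versus FF/VI is (−0.5, 0, 0.5, −0.5, 0, 0.5); UMEC 31.25 versus FF/VI is (−0.5, 0.5, 0, −0.5, 0.5, 0).
- SD of QTcF change: not in the documents. Assumed 10 to 20 msec.

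**Formula.** For a contrast c of arm means with n per arm and common SD, SE = SD × √(Σc²/n).

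- Single pair (−1, +1): Σc² = 2, so SE = SD × √(2/n).
- Pooled FF: Σc² = 4 × 0.25 = 1, so SE = SD × √(1/n).
- Ratio = √2 = 1.414, whatever n or SD. The single-pair interval is 41.4% wider; equivalently, the pooled one is 29.3% narrower.

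**95% half-widths, 1.96 × SE, for QTcF change (msec):**

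| n per arm | Assumed SD | Single pair | Pooled FF |
|---|---|---|---|
| 375 | 10 | 1.43 | 1.01 |
| 375 | 15 | 2.15 | 1.52 |
| 375 | 20 | 2.86 | 2.02 |
| 337 | 15 | 2.26 | 1.60 |
| 406.5 | 15 | 2.06 | 1.46 |

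The 337 row borrows the 10% spirometry loss; on-treatment ECG numbers at Week 24 may differ. That changes the widths but not the ratio, provided losses are similar across arms.

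**The case against.** The strongest reply is that nothing here is wrong. Section 8.6.4.1 applies the trough FEV1 method, whose primary comparisons are within FF dose, and comparing triple with dual at a matched FF dose does address the safety objective. The pooling rationale in Section 7 is written for efficacy, and neither document promises pooled safety analyses. All of this stands. A reader might infer that the SAP contradicts itself by pooling for precision in one place and not in the other, but the scope of that sentence does not support the inference.

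A second reply is that FF dose may matter for safety. Protocol 4.6.1 gives pneumonia rates of 8.5 per 1000 patient-years with FF/VI 100/25 and 18.3 with 200/25, noting wide and overlapping intervals. This is a reason to keep the within-FF results, not to omit an average beside them.

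A reader might also carry the 41% over to AEs, AESIs and MACE, or quote power gains or zero-event limits for them. The documents do not support this. No between-group interval or test is planned for those events, so none exists to be wider, and adding columns to a descriptive table would not create one. Nor is √2 general for event rates. With the two pneumonia rates above, equal person-time and no UMEC effect, the ratio is √(2 × 8.5)/√[(2 × 8.5 + 2 × 18.3)/4] = 1.13 for the FF 100 pair and √(2 × 18.3)/√[(2 × 8.5 + 2 × 18.3)/4] = 1.65 for the FF 200 pair. No count is lost either: the arms are parallel, so counts add across the two FF doses, and Table 3.4 supplies pooled exposure for the overall rates.

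Finally, SAP 2.1 refers to pooled analyses in a submission plan (SDAP). The reference sits in the key-secondary-endpoint row and does not say whether safety is covered. It would therefore go too far to say that UMEC safety is never pooled over FF dose in this programme.

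**Conclusion.** The point holds for the six modelled ECG and vital-sign endpoints in this SAP. Each reported UMEC-versus-FF/VI interval is about 41% wider than that of the pooled-FF contrast from the same six-arm model. The ratio assumes equal arms, a common variance and similar loss across arms; the msec figures also rest on an assumed SD.

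The pooled contrast is the equally weighted average of the two within-FF differences. It remains a valid estimate of that average if the UMEC effect differs by FF dose, but alone it would hide the difference.

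The 41% is measured against pooling over FF dose only and is not the limit of what the data allow: averaging over both UMEC doses as well would make the ratio 1.63. No error or bias in the plan is shown. This is a worthwhile, low-cost gain in precision.

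**What to change.** In SAP 8.6.4.1, change the sentence "Treatment comparisons 1) and 2) only as defined in Section 7 will be presented" so that it lists comparisons 1), 2), 7) and 8), with 7) and 8) obtained through the Section 7 LSMESTIMATE coefficients. Adjust the reference to unpooled data in the same section so that it describes the six-arm model and does not bar the pooled contrasts. Add the pooled contrasts to Tables 3.78 to 3.80 and 3.86 to 3.88, and keep the within-FF results there.

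The cost is two more contrasts per endpoint at each reported visit, with no new data or model. The small downside is that the pooled estimate averages over any FF-dose difference, which the retained contrasts will show.

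Optionally, add pooled-FF columns (display codes 7 to 9 in SAP 5.1) to the AESI tables 3.40 and 3.41 and the MACE tables 3.62 to 3.65, so that pooled exposure in Table 3.4 has matching event counts. This is a display convenience and should be described as such, without any precision or power claim.

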## 9. POP PK DATA SPECIFICATION

Population PK analysis will be the subject of a separate RAP and reported separately. Pop PK dataset preparation will be performed by Contract Research Organisation.

### 9.1. Pop PK Dataset Specification

General Description:

- Missing or unknown values in covariates, if not to be imputed, will be assigned -99;
- The dataset is sorted by STUDYID, SUBJID, DATETIME, EVID descending unless specify otherwise
- The data items (columns) in the analysis-ready data file will be provided the same order as follows.
- Non-numerical concentration values (such as missing samples, not assayed samples, or non-reportable samples) will not be included.

- Participants with no quantifiable concentration values will be included.
- Dosing events occurring prior to the subsequent PK sample(s) will be included (i.e., dosing events on the preceding day for pre-dose PK samples, and dosing events at the specified visit for post-dose samples)
- Liver event data will be retained in the dataset.

The dataset will be a comma delimited ASCII text file and will be named:  
NM.205715.PK.v1.csv.

Table 1 provides a list of variables required for the Pop PK dataset and format for the variables.

**Table 1 Variables required in the Pop PK (\*Mandatory variable name, included for traceability)**

Variable	Label (Variable description)	Type	Units	Missing value	Codes/Derivation/Notes
ID	NONMEM subject identifier	Integer	None	Never	Sequential subject identifier to start at PP
STUDYID*	Unique identifier for a study	Char	None	Never	205715
USUBJID*	Unique subject identifier	Char	None	Never	Identifier used to uniquely identify a subject across all studies for all applications or submissions involving the product. As in the SAS dataset.
SUBJID*	Subject identifier for study	Char	None	Never	Subject identifier, which must be unique within the study. As in the SAS dataset.
COUNTRY*	Country	Char	None	Never	Country of the investigational site in which the subject participated in the trial. e.g. USA
CNC	NONMEM Country code	Integer	None	Never	As in SAS dataset if available, otherwise generate a numerical code for each country, e.g. 1, 2,...
SITEID*	Unique identifier for a study site	Num	None	Never	e.g. PPD any lead zero should not be included.
DGRP	Actual Treatment group	Char	None	Never	As in SAS dataset e.g. FF/UMEC/VI 100/62.5/25
DOSEFF	Dose amount of FF	Num	ug	Never	Actual dose amount to be entered in all rows for each subject. e.g. DOSEFF=100 for FF/UMEC/VI 100/62.5/25
DOSEUMEC	Dose amount of UMEC	Num	ug	Never	Actual dose amount to be entered in all rows for each subject. e.g. DOSEUMEC=62.5 for FF/UMEC/VI 100/62.5/25; DOSEUMEC=0 for FF/VI 100/25

Variable	Label (Variable description)	Type	Units	Missing value	Codes/Derivation/Notes
DOSEVI	Dose amount of VI	Num	ug	Never	Actual dose amount to be entered in all rows for each subject. e.g. DOSEVI=25 for FF/UMEC/VI 100/62.5/25
VISIT	Planned Study visit	Char	none	Never	Scheduled visit, as in SAS dataset
VISITNUM	Planned study visit	Num	none	Never	Scheduled visit, as in SAS dataset, in numeric format
DAY	Study day number of record	Num	day	Never	Day of study relative to first IP dose
PTM	Planned Time	Char	None	Only for dosing records	Planned Time As in SAS dataset  Blank for dosing records.
DATETIME	Date and time of dose and PK sample	MM/DD/YYYY Y HH:MM:SS	None	Never	Date and time of dose and PK measurement record
TIME	Relative time from LAST dose to sample	Num	h	Never	Actual time from last dose of IP prior to sample.  For pre-dose sample on a visit, TIME=relative time from the dose taken at the previous day.  For dosing records, set TIME = 0.
AMTFF	NONMEM Amount of FF administered	Num	ug	Never	AMTFF=DOSEFF for rows of dosing event AMT='0' for observation rows
AMTUMEC	NONMEM Amount of UMEC administered	Num	ug	Never	AMTFF=DOSEUMEC for rows of dosing event AMT='0' for observation rows
AMTVI	NONMEM Amount of VI administered	Num	ug	Never	AMTFF=DOSEVI for rows of dosing event AMT='0' for observation rows
ANALYTE	Analyte measured	char	None	Never	As in the SMS2000 e.g. FF, UMEC, VI
RESC	Conc for corresponding ANALYTE (char)	char	pg/mL	blank	As in the SMS2000. If measurement is below LLQ, it is populated as NQ, otherwise, it is populated as the actual measurement. No sample (NS), insufficient sample (IS) and no result (NR) records will be excluded from dataset.
CONC	Conc for corresponding ANALYTE (num)	Num	pg/mL	“.”	Dosing row CONC=0. NQ will be included in the dataset but set as “.”

Variable	Label (Variable description)	Type	Units	Missing value	Codes/Derivation/Notes
LNCONC	Natural log of CONC column	Num	None	Never	If CONC=0 or CONC=".", then LNCONC='.'
LLQ	Lower Limit of quantification	Num	pg/mL	Never	Lower limit of quantification of assay. LLQ=0 for dosing rows.
LNLLQ	Natural log of LLQ	Num	None	Never	If LLQ=0, then LNLLQ='.'
LABL	Label describing the record	Char	None	Never	LABL explains the type of measurement for CONC for the current record LABL=DOSE for dosing row, LABL=CONC for observation rows.
TYPE	For handling NQ values in NONMEM	Integer			If LABL=DOSE then TYPE = 0, If CONC value present TYPE = 1 If LABL=CONC and CONC value missing TYPE = 2
MDV1	Missing data variable	Integer			0 if LABL contains CONC; 1 if LABL contains DOSE
EVID	NONMEM Event ID	Integer	None	Never	EVID=1 for LABL=DOSE, EVID=0 for LABL=CONC
II	NONMEM Inter-dose interval	Integer	Specify	Never	II=24 for dosing rows, II=0 for PK observation rows.
SS	Steady-state data item	Integer	None	Never	SS=1 for dosing records SS=0 for PK observation rows
RATE	NONMEM Rate of drug infusion	Integer	None	Never	Rate = 0 For PK observation rows, Rate = -2 for dosing records
MDV	NONMEM Missing data value	Integer	None	Never	MDV=1 for dosing records MDV=0 for CONC >0 MDV=1 for CONC="."
OCC	Occasion	Integer	None	Never	e.g. OCC=1 for Week 12 OCC=2 for Week 24 OCC=3 for Week 52 OCC=4 for Early Withdrawal
POPTXT	Subject population text	Char	None	Never	POPTXT="ASTHMA"
AGE	Subject Age	Num	Specify	-99	From source data.
SEX	Subject gender	Integer	None	Never	0=Male, 1=Female
SEXTEXT	Subject gender text	Char	None	Never	Text corresponding to code for SEX
BMI	Baseline Body Mass Index	Num	Specify	-99	From source data. Formula: Weight(kg)/(height(m)**2)
WT	Baseline Subject weight	Num	Specify	-99	From source data.
HT	Baseline Subject height	Num	Specify	-99	From source data.

Variable	Label (Variable description)	Type	Units	Missing value	Codes/Derivation/Notes
RACE	Subject race code1	Integer	None	-99	From source data e.g. 1=African American / African Heritage 2=American Indian or Alaska Native 3=Asian – Central / South Asian Heritage 4=Asian – East Asian Heritage 5=Asian – Japanese Heritage 6=Asian – South East Asian Heritage 7=Asian – Mixed Race 8=Native Hawaiian or other Pacific Islander 9=White – Arabic / North African Heritage 10=White – White / Caucasian / European Heritage 11=White – Mixed Race 12=Mixed Race
RACETXT	Subject race text	Char	None	Never	Text corresponding to code for RACE
ETHN	Subject ethnicity	Num	None	-99	From source data definition. E.g. 1=Hispanic or Latino, 2=Non-Hispanic
ETHNTEXT	Subject ethnicity text	Char	None	Never	Text corresponding to code for ETHN.
REGN	Region for subject	Num	None	-99	1 = Japan (All subjects recruited from study centres in Japan) 2 = Korea (All subjects recruited from study centres in South Korea) 3 = Rest of the World (to include all other countries)
SMOK	Subject smoking status	Integer	None	Never	0=Non-smoker, 1=Smoker, 2=Former smoker
SMOKTEXT	Subject smoking status text	Char	None	Never	Text corresponding to code for SMOK
FEV1	FEV 1 at baseline	Num	None	Never	As in the source dataset
FVC	FVC at baseline	Num	None	Never	As in the source dataset
FEV1FVC	Ratio of FEV 1 and FVC at baseline	Num	None	Never	As in the source dataset 0=>=0.7 (70%); 1=<0.7 (70%)
CRCL	Baseline Creatinine Clearance	Num	mL/min	-99	From source data. formula e.g. Creatinine Clearance will be calculated based on the Cockcroft-Gault equation. 
 
CrCL (ml/min) = [140 – AGE (in
 

Variable	Label (Variable description)	Type	Units	Missing value	Codes/Derivation/Notes
					years]]*Weight(kg)*0.85 (for female patients) / [72* Serum Creatinine (micromol/L) * 0.0113]
ALT	Alanine aminotransferase	Num		-99	Baseline defined in the source dataset
AST	Aspartate aminotransferase	Num		-99	Baseline defined in the source dataset
ALB	Albumin	Num		-99	Baseline defined in the source dataset
TBIL	Total bilirubin	Num		-99	Baseline defined in the source dataset
SCR	Serum Creatinine	Num	micro mol/L	-99	Baseline defined in the source dataset
PKSUB	PK substudy indicator	Integer			1 – if subject is in PK subset (same for all rows for the subject) 0 – if subject is not in PK subset
ERRCONT	Incorrect container indicator	Integer			1 – if subject received an incorrect container and any of the PK sampling or dosing dates/times are between the treatment start and end date (inclusive) of the incorrect container (flag only those specific PK records) 0 – otherwise
EXCREC	Exception record	Char	None	Blank	Flag for records for which the date/time and other information was obtained from the PK Exceptions Document, via data management. These records were not entered into the CRF database and correspond to samples that may have been taken in error or at an incorrect visit.

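### In SAP Table 1 the UMEC and VI amount rows assign to the FF amount variable, and the zero rule names a variable that the table does not contain

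*SAP*

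**What the plan says.** SAP Section 9 defers the population PK analysis to a separate plan but keeps the dataset specification here, and states that "Pop PK dataset preparation will be performed by Contract Research Organisation". Section 9.1 then gives Table 1, with a column for codes, derivations and notes.

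Three amount variables appear as separate rows, each marked as never missing:

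- `AMTFF`: "AMTFF=DOSEFF for rows of dosing event AMT='0' for observation rows".
- `AMTUMEC`, labelled "NONMEM Amount of UMEC administered": "AMTFF=DOSEUMEC for rows of dosing event", followed by the same zero rule for `AMT` on observation rows.
- `AMTVI`, labelled "NONMEM Amount of VI administered": "AMTFF=DOSEVI for rows of dosing event AMT='0' for observation rows".

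Earlier in the same table, `DOSEFF`, `DOSEUMEC` and `DOSEVI` are defined as separate columns that hold the actual dose on every row of a subject.

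Protocol Section 3 (repeated in SAP Section 2.2) has an objective on systemic exposure to FF, UMEC and VI, with AUC(0-τ) and Cmax as endpoints. Protocol Section 9.4.5 plans a separate nonlinear mixed-effects model for each analyte, in NONMEM or another program.

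**The concern.** In the UMEC and VI rows the variable being defined and the variable being assigned differ. Neither document contains any other rule that sets `AMTUMEC` or `AMTVI`. The observation-row rule has a related fault in all three cells: it sets `AMT`, which is not a variable in Table 1.

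The labels identify these columns as the administered amounts for NONMEM, so they are the dose input to the models behind the exposure objective. An outside organisation is to build the file. A check of that file against Table 1 would use the same faulty derivations as its reference. At stake are the FF, UMEC and VI model parameters; the primary, key secondary, other efficacy and safety results are not.

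**Working it through.** The SAP gives no figure to reproduce here. The check applies the three cells as written to a dosing row in each arm and then repeats this with the names corrected.

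**Inputs.** The arms and their doses come from SAP Section 5.1. The `DOSEFF`, `DOSEUMEC` and `DOSEVI` definitions and the three amount cells come from SAP Table 1.

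**Step 1: what each cell sets on a dosing row.**

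| Row | Variable the row defines | Variable the cell sets | Source |
|---|---|---|---|
| FF amount | `AMTFF` | `AMTFF` | `DOSEFF` |
| UMEC amount | `AMTUMEC` | `AMTFF` | `DOSEUMEC` |
| VI amount | `AMTVI` | `AMTFF` | `DOSEVI` |

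Regardless of order, `AMTUMEC` and `AMTVI` are never set, and `AMTFF` has three definitions that cannot all hold.

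**Step 2: result if the cells run from top to bottom.** This order is an assumption. The SAP fixes the order of columns in the output file, not an order of assignments.

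| Arm | `AMTFF` after FF row | after UMEC row | after VI row | Intended `AMTFF` / `AMTUMEC` / `AMTVI` | Intended ÷ final `AMTFF` |
|---|---|---|---|---|---|
| FF/VI 100/25 | 100 | 0 | 25 | 100 / 0 / 25 | 100/25 = 4 |
| FF/VI 200/25 | 200 | 0 | 25 | 200 / 0 / 25 | 200/25 = 8 |
| FF/UMEC/VI 100/31.25/25 | 100 | 31.25 | 25 | 100 / 31.25 / 25 | 4 |
| FF/UMEC/VI 200/31.25/25 | 200 | 31.25 | 25 | 200 / 31.25 / 25 | 8 |
| FF/UMEC/VI 100/62.5/25 | 100 | 62.5 | 25 | 100 / 62.5 / 25 | 4 |
| FF/UMEC/VI 200/62.5/25 | 200 | 62.5 | 25 | 200 / 62.5 / 25 | 8 |

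The ratio of the high to the low FF amount falls from 200/100 = 2 to 25/25 = 1.

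**Step 3: consequence for the FF parameters.** In a linear model, concentrations depend on the amount divided by apparent clearance (CL/F), and likewise for apparent volume. If the amount entered is a fraction r of the true one, the fit reproduces the observed concentrations with CL/F and V/F multiplied by r. Here r = 25/100 = 0.25 in the FF 100 arms and r = 25/200 = 0.125 in the FF 200 arms. Because r differs between the two, no single clearance can absorb the error.

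**Step 4: consequence for exposure.** Take AUC over a dosing interval at steady state as amount ÷ (CL/F).

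- If the same wrong amount is used throughout, the error cancels within an arm: 25 ÷ (0.25 × CL/F) = 100 ÷ (CL/F).
- If AUC is computed from `DOSEFF` and a clearance fitted to `AMTFF`, it does not cancel: 100 ÷ (0.25 × CL/F) is 4 times the true value, and 200 ÷ (0.125 × CL/F) is 8 times.

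Which route applies is a matter for the separate population PK plan, which is not among these documents.

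**Step 5: observation rows.** The cells set `AMT` to zero. Table 1 has no such column, so read literally the zero rule applies to none of the three amount variables.

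**The case against.** The strongest reply is that this is a copy-paste slip with only one sensible reading. Each row carries its own variable name and label, and the right-hand sides are correct. A PK programmer would take `AMT` as shorthand for the row's own amount column. A literal build would leave two mandatory columns empty and so would fail visibly. All of this is reasonable, and it is why the point is minor. It does not make the cells right: they are the only derivations given for these columns. Damage from reading the PDF is also unlikely, because the rows are otherwise intact and the same wrong name sits inside two otherwise correct formulas.

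Three stronger readings are tempting, and the documents do not support them.

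- A reader might infer that the FF dose itself is lost. It is not. `DOSEFF`, `DOSEUMEC` and `DOSEVI` are correctly specified on every row and the actual treatment group is a further column, so a mismatch with `AMTFF` shows within the row.
- A reader might infer that a 4- to 8-fold error will certainly enter the file. That needs a top-to-bottom build, which the SAP does not describe.
- A reader might infer that AUC(0-τ) and Cmax would be wrong by the same factor. Step 4 shows that this depends on how exposure is computed, which these documents leave open.

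**Conclusion.** Wrong as written, minor severity. Two results need no assumption beyond a literal reading: `AMTUMEC` and `AMTVI` have no usable assignment although they may not be missing, and `AMTFF` is defined in three conflicting ways. The 25 mcg end value, the 4- and 8-fold ratios and the lost FF contrast hold only if the cells are applied in table order. The distortion of apparent FF clearance and volume further assumes a linear model fitted to that column.

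The error can be found and reversed from columns in the same file. PK is outside the multiplicity hierarchy in SAP Section 5.6, and no efficacy or safety analysis uses these columns.

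**What to change.** In SAP Table 1:

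- On dosing rows, set `AMTUMEC` = `DOSEUMEC` and `AMTVI` = `DOSEVI`. The rule `AMTFF` = `DOSEFF` stays.
- On observation rows, replace `AMT` with `AMTFF`, `AMTUMEC` and `AMTVI` in their respective rows, each set to 0.

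With these changes a dosing row for FF/UMEC/VI 100/62.5/25 gives 100, 62.5 and 25, and one for FF/VI 100/25 gives 100, 0 and 25, as intended. If the file has already been built, comparing each amount column with its dose column on dosing rows will show whether the slip was carried through.

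The cost is two corrected left-hand names and one variable name in each of three zero rules. No new data and no change to trial conduct are needed.
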